8.3. Accounting for missing, unavailable or doubtful data, outliers

All information specified in the e-CRFs should be supported by relevant data in source documents.

After entering all data into the electronic database, a database specialist checks it for inconsistencies, errors, and missing data points. The Clinical Study Database Manager or Medical Expert of JSC BIOCADC generates queries to correct error data or to request missing data; the queries are site-specific and subject-specific (i.e., individual queries are generated for each subject). The Clinical Study Monitor will send queries to the study site by fax or email. The queries should be resolved by the investigator within five business days from the date they have been submitted to the study site. Copies of responses to queries must be kept at the study site; original responses must be stored at JSC BIOCADC.

When responses to queries are received from investigators, the database specialist checks it for inconsistencies, errors, and missing data points. When all data at all study sites have been collected and entered, the database is closed. Afterwards, statistical processing can be started.

Missing, unused, and spurious data will not be substituted.

Spurious and unevaluable data are revealed during the outlier analysis by examination of Mahalanobis or Cook distance, visual analysis of scatter plots and box plots.

All actions taken to handle missing, unevaluable, spurious data and outliers before/during the statistical analysis will be described in the Clinical Study Report.

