7. STATISTICAL ANALYSIS OF POPULATION

Pharmacokinetics analysis

The pharmacokinetics (PK) analysis will include data of all volunteers who have received one dose of BCD-131 or reference drugs. If a subject has had more than two PK serum samples missed / lost / spoilt and skipped blood sampling time points more than twice, his/her data will not be included in the PK analysis.

Pharmacodynamics analysis

The pharmacodynamics (PD) analysis will include data of all volunteers who have received one dose of BCD-131 or reference drugs. If a subject has had more than two PK serum samples missed / lost / spoilt and skipped blood sampling time points more than twice, his/her data will not be included in the PD analysis.

Safety analysis

The safety analysis will include all patients who have received one dose of the test/reference drug.

Immunogenicity analysis

The immunogenicity analysis will include data of all volunteers who have received one dose of BCD-131 or reference drugs. If a subject has had serum samples taken on Day 1 and Day 50 missed / lost / spoilt, his/her data will not be included in the immunogenicity analysis.

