8.4. The data conversion

Pharmacokinetic parameters

Based on determined concentrations in blood a number of the pharmacokinetic parameters will be calculated for the study drug:

1. **AUC₍₀₋₁₁₇₆₎**— area under the plasma concentration curve from administration to 1176 h:

- At stage I for BCD-131 and Mircera® products:

$$AUC_{(0-1176)} = \sum_{p=2}^{18} \frac{(C_p + C_{p-1}) * (t_p - t_{p-1})}{2},$$

where C_p – plasma concentration at the moment t_p (hours); $t_p \in \{0; 0.5; 2; 8; 24; 48; 72; 96; 120; 168; 216; 288; 336; 504; 672; 840; 1008; 1176\}; p=1, \dots, 18$

- At stage I for Aranesp® product:

$$AUC_{(0-1176)} = \sum_{p=2}^{20} \frac{(C_p + C_{p-1}) * (t_p - t_{p-1})}{2},$$

where C_p – plasma concentration at the moment t_p (hours); $t_p \in \{0; 0.5; 2; 8; 16; 24; 36; 48; 72; 96; 120; 168; 216; 288; 336; 504; 672; 840; 1008; 1176\}; p=1, \dots, 20$

- At stage II:

$$AUC_{(0-1176)} = \sum_{p=2}^{21} \frac{(C_p + C_{p-1}) * (t_p - t_{p-1})}{2},$$

where C_p – plasma concentration at the moment t_p (hours); $t_p \in \{0; 0.25; 0.5; 1; 2; 4; 8; 24; 48\}$

72; 96; 120; 168; 216; 288; 336; 504; 672; 840; 1008; 1176}; $p=1, \dots, 21$

2. C_{max} - maximum plasma concentration.
3. T_{max} - time until C_{max} is reached.
4. **Terminal rate constant (k_{el} , elimination constant)** will be calculated for the plasma concentration curve during the terminal log-linear phase by regression.
5. **AUC_(0-∞)** - area under the plasma concentration curve from administration to infinity:

$$AUC_{(0-\infty)} = AUC_{(0-1176)} + \frac{C_{1176}}{k_{el}},$$

where C_{1176} - plasma concentration at the moment 1176 h; k_{el} - elimination constant.

6. **Plasma concentration half-life ($T_{1/2}$)** will be calculated as:
 $T_{1/2} = \frac{\ln(2)}{k_{el}}$, where k_{el} - elimination constant.
7. **Total clearance (CL)** will be calculated as:

$$CL = \frac{D}{AUC_{(0-1176)}}, \quad \text{where } D \text{ - single dose of the drug product.}$$

Pharmacodynamic parameters

Based on reticulocyte counts and on hemoglobin values a number of key pharmacodynamic parameters will be calculated:

1. **AUEC₍₀₋₁₁₇₆₎** - (area under effect curve from the moment of injection to 1176 h [Day 50 of follow-up]) based on the change in the absolute reticulocyte count after a single-dose injection of the drug product::

$$AUEC_{(0-1176)} = \sum_{p=2}^{15} \frac{(C_p + C_{p-1}) * (t_p - t_{p-1})}{2},$$

where C_p the absolute reticulocyte count at the moment t_p (hours);

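### AUC and AUEC have no defined value for volunteers kept in the analysis with a lost sample, and the whole-subject exclusion rule discards PK parameters that are still valid

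*SAP*

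**What the plan says.** **Who is analysed.** Under SAP 7 the PK "analysis will include data of all volunteers who have received one dose of BCD-131 or reference drugs". A volunteer leaves only after "more than two PK serum samples missed / lost / spoilt and skipped blood sampling time points more than twice", and then "his/her data will not be included in the PK analysis". Volunteers with one or two lost tubes therefore stay. The PD set uses the same trigger, a count of PK tubes. The Protocol carries both rules (Statistical Analysis, PK analysis and PD analysis).

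**How AUC is formed.** SAP 8.4 gives a linear trapezoidal sum over fixed nominal times. For BCD-131 and Mircera at stage I these are "0; 0.5; 2; 8; 24; 48; 72; 96; 120; 168; 216; 288; 336; 504; 672; 840; 1008; 1176" h. Aranesp has 20 times, stage II has 21, and AUEC (reticulocytes and Hb) has 15. AUC(0-∞) adds the 1176 h concentration divided by kel.

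**What happens to gaps.** SAP 8.3: "Missing, unused, and spurious data will not be substituted". It adds that actions taken on missing data will be described in the study report. No section says how a sum is formed when one of its concentrations is absent.

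**The concern.** Each rule is reasonable alone, but together they leave a gap. The set definition expects some incomplete profiles, the formula needs every point, and the missing-data rule supplies none. An analyst could set the AUC to missing, drop the affected terms or join the neighbouring measured points. The results differ widely, and the choice would be made after the data are seen.

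AUC and reticulocyte AUEC are primary endpoints, and the stage I comparison is used to choose the stage II dose. With the obligatory three volunteers, one person is a third of a dose level; in a reference group of six, one is 16.7%.

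The exclusion rule has the opposite weakness. It acts on the whole subject, so a volunteer who misses only late visits also loses Cmax and Tmax, which those visits do not determine.

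**Working it through.** **1. The plan's own counts.** The listed times number 18, 20, 21 and 15, matching the summation limits in SAP 8.4. They give 17, 19, 20 and 14 trapezoids.

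**2. Terms touched by one lost sample.** Every interior sample enters two trapezoids; the first and last enter one. Hours left uncovered if those terms are absent, stage I BCD-131/Mircera grid:
- 168 h sample: 216 − 120 = 96 h, 96/1176 = 8.2%
- 336 h sample: 504 − 288 = 216 h, 18.4%
- 504 h sample: 672 − 336 = 336 h, 28.6% (the same span and share for 672, 840 and 1008 h)

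The AUEC grid has the same spacing from 24 h on, so a missing 504 h count also leaves 28.6% of the window uncovered. That figure needs no PK assumption.

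**3. Share of AUC.** The documents give no PK values, so profiles are assumed: C(t) = ka/(ka − k) × (e^(−kt) − e^(−ka·t)), scaled to dose/volume = 1, with half-life/absorption half-life of 72/48.5, 100/40 and 140/60 h. On the stage I grid they peak at 96, 96 and 120 h.

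Worked case, 72/48.5 profile, 504 h lost. C(336) = 0.0955, C(504) = 0.0217, C(672) = 0.0045; full AUC = 105.4.
- The two terms: (0.0955 + 0.0217) × 168/2 + (0.0217 + 0.0045) × 168/2 = 9.84 + 2.20 = 12.05. Dropped: −12.05/105.4 = −11.4%.
- Neighbours joined: (0.0955 + 0.0045) × 336/2 = 16.8. Change: (16.8 − 12.05)/105.4 = +4.5%.

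The same calculation for other losses (change in AUC for the three profiles in the order above):

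| Lost sample(s), h | Terms dropped, % | Neighbours joined, % |
|---|---|---|
| 8 | −3.1 / −2.7 / −1.4 | −0.1 / −0.1 / 0.0 |
| 168 | −30.0 / −28.1 / −23.7 | −0.1 / −0.1 / −0.4 |
| 288 | −18.5 / −19.6 / −22.2 | +0.7 / +0.5 / +0.1 |
| 336 | −14.7 / −18.1 / −25.7 | +2.0 / +1.6 / +0.7 |
| 504 | −11.4 / −15.7 / −26.3 | +4.5 / +4.2 / +3.3 |
| 672 | −2.5 / −5.0 / −12.0 | +1.1 / +1.4 / +1.7 |
| 840 | −0.5 / −1.6 / −5.3 | +0.2 / +0.4 / +0.8 |
| 1008 | −0.1 / −0.5 / −2.3 | 0.0 / +0.1 / +0.4 |
| 504 and 672 | −11.9 / −16.9 / −30.0 | +11.2 / +11.0 / +10.1 |
| 672, 840 and 1008 | −2.6 / −5.5 / −14.3 | +4.3 / +6.2 / +9.5 |

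Since SAP 8.4 sets CL = D/AUC(0-1176), a loss of 11.4% to 30.0% would raise CL by 1/0.886 − 1 = 13% to 1/0.700 − 1 = 43%.

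**4. Wider assumptions.** With half-life 50 to 200 h and absorption half-life 15 to 45 h, the worst single tube carries 22.7% to 36.3% of AUC if its terms are dropped. Joining neighbours changes AUC by −4.1% to +4.3%.

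**5. The last tube.** A lost 1176 h sample costs at most 1.8% of AUC(0-1176) across the wider range. It leaves AUC(0-∞) undefined, because the formula names that concentration.

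**6. The exclusion rule.** A volunteer who skips 672, 840 and 1008 h meets both conditions and leaves the PK set. The peak lies at 96 to 120 h in these profiles, so Cmax and Tmax are unaffected, yet both are discarded.

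**The case against.** A reader might infer that the SAP removes two trapezoids for each lost tube and so biases AUC low. The documents do not say that. SAP 8.4 gives the formula for a complete profile. Not substituting is most naturally read as not imputing a concentration, and joining two measured points imputes none. A sensible analyst could join them without breaching SAP 8.3. That stands: the percentages in the dropped column describe one possible reading, not the plan.

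The loss also depends heavily on which tube is missing. It is at most about 5% at 8 h or earlier and at 840 or 1008 h, and 2.5% to 12.0% at 672 h. Joining is not always the more accurate choice: with 672, 840 and 1008 h missing in the 72/48.5 profile, dropping costs 2.6% while joining adds 4.3%.

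A reader might also conclude that the exclusion rule should join its conditions with or in place of and. Literally, a volunteer with three or more spoilt tubes but no more than two skipped time points stays in. Changing the conjunction would exclude more volunteers and worsen the loss of valid parameters, so it is not recommended. The present wording also means that whole-subject exclusion will arise less often.

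Finally, SAP 8.3 provides for data queries and for reporting the actions taken. That gives transparency afterwards, but not a rule beforehand.

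**Conclusion.** The point holds as a gap between stated rules. A volunteer kept in the set with a missing sample has no defined AUC or AUEC, and an excluded volunteer loses parameters that could be validly reported. Taken alone, the missing-tube gap is close to missing detail. Together with the whole-subject exclusion, in cohorts of as few as three, it justifies a change to the plan.

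If terms were dropped, one tube at 168 to 504 h would cost about 11% to 30% of AUC. This rests on assumed one-compartment profiles with half-lives of 72 to 140 h. The coverage figures and the undefined AUC(0-∞) follow from the documents alone.

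**What to change.** **SAP 8.4.** Compute AUC and AUEC by linear trapezoids between consecutive measured samples at recorded times. Extrapolate AUC(0-∞) from the last measurable concentration, so that a lost 1176 h tube is covered.

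**SAP 7 and the Protocol's PK analysis paragraph.** Replace the whole-subject PK exclusion by evaluability per parameter:
- Cmax and Tmax: keep when the samples around the observed peak are present.
- AUC: keep, and flag when a bridged gap is long; state the length that triggers the flag.
- kel, T1/2 and AUC(0-∞): report only with at least three terminal points.

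The matching PD paragraphs should count PD samples, since they now remove PD data on a count of PK tubes. If the Protocol is not amended, declare the change in SAP 10, which now states that there are no deviations.

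**Cost.** SAP wording, standard programming, and a Protocol change or declared deviation. Joining a gap overestimates AUC by up to about 5% for one tube and about 11% for two adjacent late tubes (504 and 672 h) in the assumed profiles. With a sharper peak it can understate by about 4%. The number of volunteers will differ by parameter and should be shown in each table.

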8.4. The data conversion

Pharmacokinetic parameters

Based on determined concentrations in blood a number of the pharmacokinetic parameters will be calculated for the study drug:

1. **AUC₍₀₋₁₁₇₆₎**— area under the plasma concentration curve from administration to 1176 h:

- At stage I for BCD-131 and Mircera® products:

$$AUC_{(0-1176)} = \sum_{p=2}^{18} \frac{(C_p + C_{p-1}) * (t_p - t_{p-1})}{2},$$

where C_p – plasma concentration at the moment t_p (hours); $t_p \in \{0; 0.5; 2; 8; 24; 48; 72; 96; 120; 168; 216; 288; 336; 504; 672; 840; 1008; 1176\}; p=1, \dots, 18$

- At stage I for Aranesp® product:

$$AUC_{(0-1176)} = \sum_{p=2}^{20} \frac{(C_p + C_{p-1}) * (t_p - t_{p-1})}{2},$$

where C_p – plasma concentration at the moment t_p (hours); $t_p \in \{0; 0.5; 2; 8; 16; 24; 36; 48; 72; 96; 120; 168; 216; 288; 336; 504; 672; 840; 1008; 1176\}; p=1, \dots, 20$

- At stage II:

$$AUC_{(0-1176)} = \sum_{p=2}^{21} \frac{(C_p + C_{p-1}) * (t_p - t_{p-1})}{2},$$

where C_p – plasma concentration at the moment t_p (hours); $t_p \in \{0; 0.25; 0.5; 1; 2; 4; 8; 24; 48\}$

72; 96; 120; 168; 216; 288; 336; 504; 672; 840; 1008; 1176}; $p=1, \dots, 21$

2. C_{max} - maximum plasma concentration.
3. T_{max} - time until C_{max} is reached.
4. **Terminal rate constant (k_{el} , elimination constant)** will be calculated for the plasma concentration curve during the terminal log-linear phase by regression.
5. **AUC_(0-∞)** - area under the plasma concentration curve from administration to infinity:

$$AUC_{(0-\infty)} = AUC_{(0-1176)} + \frac{C_{1176}}{k_{el}},$$

where C_{1176} - plasma concentration at the moment 1176 h; k_{el} - elimination constant.

6. **Plasma concentration half-life ($T_{1/2}$)** will be calculated as:
 $T_{1/2} = \frac{\ln(2)}{k_{el}}$, where k_{el} - elimination constant.
7. **Total clearance (CL)** will be calculated as:

$$CL = \frac{D}{AUC_{(0-1176)}}, \quad \text{where } D \text{ - single dose of the drug product.}$$

Pharmacodynamic parameters

Based on reticulocyte counts and on hemoglobin values a number of key pharmacodynamic parameters will be calculated:

1. **AUEC₍₀₋₁₁₇₆₎** - (area under effect curve from the moment of injection to 1176 h [Day 50 of follow-up]) based on the change in the absolute reticulocyte count after a single-dose injection of the drug product::

$$AUEC_{(0-1176)} = \sum_{p=2}^{15} \frac{(C_p + C_{p-1}) * (t_p - t_{p-1})}{2},$$

where C_p the absolute reticulocyte count at the moment t_p (hours);

$t_p \in \{ 0; 24; 48; 72; 96; 120; 168; 216; 288; 336; 504; 672; 840; 1008; 1176 \}; p=1, \dots, 15$

2. **AUEC₍₀₋₁₁₇₆₎** - (area under effect curve from the moment of injection to 1176 h [Day 50 of follow-up]) based on the change in the Hb level in the blood after a single-dose injection of the drug product:

$$AUEC_{(0-1176)} = \sum_{p=2}^{15} \frac{(C_p + C_{p-1}) * (t_p - t_{p-1})}{2},$$

where C_p the Hb level at the moment t_p (hours);

$t_p \in \{ 0; 24; 48; 72; 96; 120; 168; 216; 288; 336; 504; 672; 840; 1008; 1176 \}; p=1, \dots, 15$

3. AC-E_{max} (absolute maximum increase in the test parameter vs. baseline) based on the change in the absolute reticulocyte count in the blood after a single-dose injection of the drug product.
4. AC-E_{max} (absolute maximum increase in the test parameter vs. baseline) based on the change in the Hb level in the blood after a single-dose injection of the drug product.

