Time Points for Blood Sampling to Evaluate PK at Stage I of the Study	In the groups of volunteers receiving BCD-131 and Mircera®, blood sampling for the PK evaluation will be performed as follows: 

1. PK1-1 — 5 min before the injection of BCD-131/Mircera®

2. PK2-1 — 30 ± 5 min after the injection of BCD-131/Mircera®

3. PK3-1 — 2 h ± 10 min after the injection of BCD-131/Mircera®

4. PK4-1 — 8 h ± 15 min after the injection of BCD-131/Mircera®

5. PK5-1 — 24 h ± 20 min after the injection of BCD-131/Mircera®

6. PK6-1 — 48 h ± 30 min after the injection of BCD-131/Mircera®

	

7. PK7-1 — 72 h ± 30 min after the injection of BCD-131/Mircera®

8. PK8-1 — 96 h ± 60 min after the injection of BCD-131/Mircera®

9. PK9-1 — 120 h ± 60 min after the injection of BCD-131/Mircera®

10. PK10-1 — 168 h ± 60 min after the injection of BCD-131/Mircera®

11. PK11-1 — 216 h ± 120 min after the injection of BCD-131/Mircera®

12. PK12-1 — 288 h ± 120 min after the injection of BCD-131/Mircera®

13. PK13-1 — 336 h ± 120 min after the injection of BCD-131/Mircera®

14. PK14-1 — 504 h ± 120 min after the injection of BCD-131/Mircera®

15. PK15-1 — 672 h ± 120 min after the injection of BCD-131/Mircera®

16. PK16-1 — 840 h ± 120 min after the injection of BCD-131/Mircera®

17. PK17-1 — 1008 h ± 120 min after the injection of BCD-131/Mircera®

18. PK18-1 — 1176 h ± 120 min after the injection of BCD-131/Mircera®

--	---

In the group of volunteers receiving Aranesp®, blood sampling for the PK evaluation will be performed as follows:

1. PK1-1 — 5 min before the injection of Aranesp®
2. PK2-1 — 30 ± 5 min after the injection of Aranesp®
3. PK3-1 — 2 h ± 10 min after the injection of Aranesp®
4. PK3-1 — 8 h ± 15 min after the injection of Aranesp®
5. PK5-1 — 16 h ± 20 min after the injection of Aranesp®
6. PK6-1 — 24 h ± 20 min after the injection of Aranesp®
7. PK7-1 — 36 h ± 30 min after the injection of Aranesp®
8. PK8-1 — 48 h ± 30 min after the injection of Aranesp®
9. PK9-1 — 72 h ± 30 min after the injection of Aranesp®
10. PK10-1 — 96 h ± 60 min after the injection of Aranesp®
11. PK11-1 — 120 h ± 60 min after the injection of Aranesp®
12. PK12-1 — 168 h ± 60 min after the injection of Aranesp®
13. PK13-1 — 216 h ± 120 min after the injection of Aranesp®

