Subjects will be asked to stay at the study site for the first 24 h after the injection because multiple blood samples are to be collected over this period.

Regardless of the group/cohort to which a volunteer has been assigned, s/he will be followed-up for 50 days during which 16 visits will be performed.

Stage II

Stage II of the study aims to further evaluate pharmacokinetics, pharmacodynamics and safety of subcutaneous and intravenous injections of BCD-131 at a dose which ensures PD effects similar to those of the closest analogues (Mircera[®], Aranesp[®]) given as subcutaneous injections at therapeutic doses. For this purpose, 12 volunteers will be included in the study after they have signed an informed consent form, completed an examination at screening (no more than 14 days) and received the approval of the investigator confirming their eligibility for the study.

After having been randomized in a 1:1 ratio, the volunteers will be assigned to 2 groups.

- Six volunteers in Group 1 will receive a single intravenous injection of BCD-131 at a dose established at stage I of the study (Day 1).
- Six volunteers in Group 2 will receive a single subcutaneous injection of BCD-131 at a dose established at stage I of the study (Day 1).

Subjects will be asked to stay at the study site for the first 24 h after the injection because multiple blood samples are to be collected over this period. Regardless of the group/cohort to which a volunteer has been assigned, s/he will be followed-up for 50 days during which 16 visits will be performed.

3.2 Time Points for Blood Sampling to Evaluate PK at Stage I of the Study

In the groups of volunteers receiving BCD-131 and Mircera[®], blood sampling for the PK evaluation will be performed as follows:

1. PK1-1 — 5 min before the injection of BCD-131/Mircera[®]
2. PK2-1 — 30 ± 5 min after the injection of BCD-131/Mircera[®]
3. PK3-1 — $2 \text{ h} \pm 10 \text{ min}$ after the injection of BCD-131/Mircera[®]
4. PK4-1 — $8 \text{ h} \pm 15 \text{ min}$ after the injection of BCD-131/Mircera[®]
5. PK5-1 — $24 \text{ h} \pm 20 \text{ min}$ after the injection of BCD-131/Mircera[®]
6. PK6-1 — $48 \text{ h} \pm 30 \text{ min}$ after the injection of BCD-131/Mircera[®]
7. PK7-1 — $72 \text{ h} \pm 30 \text{ min}$ after the injection of BCD-131/Mircera[®]
8. PK8-1 — $96 \text{ h} \pm 60 \text{ min}$ after the injection of BCD-131/Mircera[®]
9. PK9-1 — $120 \text{ h} \pm 60 \text{ min}$ after the injection of BCD-131/Mircera[®]

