3.4.2. Inclusion criteria

1. Signing of the Informed Consent Form;
2. Male sex;
3. Age of 18 to 45 years, inclusive;
4. BMI within normal limits (18.5–24.9 kg/m²);
5. Healthy patients, which is proved by their medical history, physical examination and laboratory findings:
 - No clinically significant abnormalities of circulatory, respiratory, nervous, hematopoietic, endocrine and digestive systems, liver and kidneys in the past medical history and at screening;
 - No history of cardiovascular disorders or thyroid disorders;
 - No history of hematologic disorders, including but not limited to any type of anemia, myelodysplastic syndrome, blood cancers, hemolytic syndrome, hemoglobinopathies, coagulopathies;
 - CBC results within normal limits, including:
 - Hemoglobin within 132–173 g/L;
 - Hematocrit (based on CBC results) within 39–49%;
 - Platelet count within 150–400*10⁹/L;
 - Absolute reticulocyte count within 30.4–93.5 * 10⁹/L;
 - Blood biochemistry and urinalysis results within normal limits;
 - Serum ferritin within 20–250 µg/L;
 - Serum endogenous erythropoietin within 4.3–29.0 MIU/mL;
 - Hemodynamic parameters within normal limits: systolic blood pressure within 100–139 mmHg; diastolic blood pressure within 60–90 mmHg; heart rate within 50–90 bpm;
 - No history of chronic infections (tuberculosis) or chronic inflammation;
 - No hepatitis B or C, HIV, or syphilis;
 - No acute infections within 4 weeks prior to inclusion in the study;
 - No psychiatric disorders and other conditions (including depression) that can interfere with the volunteer's ability to follow the study protocol;

- Well-being (in the volunteer's opinion) within 30 days prior to inclusion in the study;
- 6. No history of or current (at baseline) alcohol or drug abuse;
- 7. Ability of the volunteer, in the investigator's opinion, to follow the study protocol procedures;
- 8. Willingness of volunteers and their sexual partners with preserved reproductive potential to use reliable contraception within 2 weeks before inclusion in the study and up to 7 weeks after the injection of the test product. This criterion is not applicable to subjects who underwent surgical sterilization. Reliable methods of contraception include one barrier method in combination with one of the following methods: spermicides, intrauterine device/oral contraceptives (for sexual partners).

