4. EVALUATION CRITERIA

4.1 Endpoints to Evaluate Single-Dose Pharmacokinetics

Primary endpoint

- $AUC_{0-1176\text{ h}}$ (area under the concentration vs. time curve from the moment of injection to 1176 h [Day 50 of follow-up]) and $AUC_{0-\infty}$ (to infinity).

Secondary endpoints

- C_{\max} (maximum serum concentration),
- T_{\max} (time to C_{\max}),
- $T^{1/2}$ (half-life),

- k_{el} (elimination constant),
- CL (total clearance).

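### SAP 8.4 derives the primary PK parameters from raw concentrations, with no rule for endogenous erythropoietin and no statement of whether the assays read it

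*SAP*

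**What the plan says.** The primary PK endpoints in SAP 4.1 are AUC(0-1176), the "area under the concentration vs. time curve from the moment of injection to 1176 h", and AUC(0-∞). Cmax, Tmax, T1/2, kel and CL are secondary.

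SAP 8.4 bases them on measured concentrations: "Based on determined concentrations in blood a number of the pharmacokinetic parameters will be calculated for the study drug". AUC(0-1176) is a linear trapezoid in which each term is the "plasma concentration at the moment t_p (hours"), starting at time 0. The only sample that can supply the time-0 value is the pre-dose one, which SAP 3.2 lists as "PK1-1 — 5 min before the injection of BCD-131/Mircera". Equivalent pre-dose samples are listed for Aranesp and for stage II. From the same uncorrected curve, the SAP takes:

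- kel by regression over the terminal log-linear phase, with no rule for choosing the points
- T1/2 = ln 2 / kel
- AUC(0-∞) = AUC(0-1176) + C(1176)/kel
- CL = dose / AUC(0-1176)

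SAP 3.4.2 requires "Serum endogenous erythropoietin within 4.3–29.0 MIU/mL" at entry, and the protocol synopsis has the same criterion. No section subtracts a pre-dose value, says what to do if it is measurable, or states the analyte, specificity or lower limit of quantification (LLOQ) of any PK assay. SAP 8.4 does define the PD parameter AC-Emax against baseline. No PK parameter is defined that way.

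**The concern.** The test drug and both comparators are erythropoietin-type proteins given to people who already have erythropoietin in their blood. If an assay cannot tell the two apart, every measured concentration is drug plus the volunteer's own hormone. That addition does not scale with dose, while the planned doses span 89-fold (4.45 / 0.05).

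Three consequences would follow. Exposure per unit dose would look highest in the lowest cohorts, which blurs any reading of dose proportionality. Late samples would settle on the endogenous level instead of falling to zero, so kel would be too small and T1/2 and the extrapolated area too large, and half-life would seem to shorten as dose rises. Comparisons between products would be distorted if their assays cross-react to different degrees. The low cohorts may hold only three volunteers each, and permitted entry levels differ 6.7-fold (29.0 / 4.3), so the addition could also vary widely within a cohort.

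**Working it through.** The plan states no figure that this point can be checked against, so the check applies the SAP's own formulas to a constant addition.

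**1. Area added by a constant.** A linear trapezoid integrates a constant B exactly, so the addition to AUC(0-1176) is B × 1176 h on any of the three sampling grids. If the assay reads native hormone fully and in the units of the entry criterion:

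- 4.3 × 1176 = 5,057 mIU·h/mL
- 29.0 × 1176 = 34,104 mIU·h/mL

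The documents give no PK units or expected concentrations, so these areas cannot be set against any study AUC. The rest therefore uses R, the ratio of peak drug concentration to baseline.

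**2. Assumed profile.** None of these inputs is in the documents: one compartment, subcutaneous absorption half-life 24 h, true T1/2 of 70, 140 or 200 h, endogenous level constant, full cross-reactivity. The profile is evaluated at the 18 nominal stage I times for BCD-131 and Mircera. The drug-only AUC(0-1176) divided by peak is 178.4, 292.8 and 380.5 h for the three half-lives.

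**3. Inflation of AUC(0-1176)** = (1176 / R) / (AUC/peak). For R = 20 and 70 h: (1176 / 20) / 178.4 = 58.8 / 178.4 = 33%.

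| Peak ÷ baseline | T1/2 70 h | T1/2 140 h | T1/2 200 h |
|---|---|---|---|
| 200 | 3.3% | 2.0% | 1.5% |
| 20 | 33% | 20% | 15% |
| 5 | 132% | 80% | 62% |

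CL is divided by one plus the same fraction. At R = 20 it is therefore 0.75 to 0.87 of its true value.

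**4. Half-life, true value 140 h.** SAP 8.4 does not say which samples form the terminal phase, so two windows are shown.

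| Peak ÷ baseline | kel on 504–1176 h | kel on 120–336 h |
|---|---|---|
| no endogenous hormone | 140 h | 147 h |
| 200 | 172 h | 148 h |
| 20 | 375 h | 161 h |
| 5 | 936 h | 202 h |

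**5. AUC(0-∞)**, with kel on 504–1176 h: inflated by 2–5% at R = 200 and 22–102% at R = 20 across the three half-lives. These figures inherit the dependence on the fitting window.

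**6. When the constant is more than half of AUC(0-1176).** This needs inflation above 100%, that is R below 1176 / (AUC/peak): 1176 / 178.4 = 6.6, 1176 / 292.8 = 4.0 and 1176 / 380.5 = 3.1 for the three half-lives. Of the cases tabulated, only R = 5 with a 70 h half-life qualifies.

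**The case against.** The strongest reply is that everything hangs on an assay nobody reading these documents can see. The protocol text supplied is a synopsis, and a bioanalytical description may exist elsewhere. With a specific assay there is no bias at all. This stands, and it makes the point conditional. It does not remove it, because SAP 8.4 gives one fixed set of formulas and no branch for a measurable pre-dose value. The closing paragraph of SAP 8.2 lets methods be added after data collection, so in an open-label study the choice would be made with the concentrations in view.

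The half-life figures can also be challenged. A late window that has flattened onto a plateau is not a log-linear decline, and a careful analyst might not use it. That stands too: on 120–336 h most of the distortion disappears. Some remains (161 h against 147 h at 20 times), and the SAP does not say which window applies.

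Two stronger readings are tempting:

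- *A reader might infer that low-dose exposure is mostly the volunteer's own hormone.* The documents give no concentrations, so R cannot be tied to a dose. Doing so needs more assumptions: volume 50 mL/kg, absorption rate 0.03/h, half-life 70 or 140 h, bioavailability 0.5 or 1.0, and 130 IU/µg. With full cross-reactivity, the endogenous share of AUC(0-1176) at 0.05 µg/kg is then 16–43% at the low entry limit and 56–84% at the high limit. With 10% cross-reactivity it is 2–34%, never a majority.
- *A reader might infer that the stage II dose will be wrong.* SAP 3.1 does include PK in the stage I comparison, but the dose sought is the one with PD effects similar to the comparators. PK AUC is not the selection criterion.

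Finally, subtracting one pre-dose value assumes that endogenous hormone stays constant after dosing. It may not, so the corrected result should accompany the uncorrected one.

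**Conclusion.** The gap is real and the harm is conditional. SAP 8.4 derives both primary PK endpoints, and kel, T1/2 and CL with them, from raw concentrations. The entry criteria guarantee circulating native hormone, and a pre-dose sample is drawn but never used as a baseline. If a product's assay reads native hormone, the primary endpoints are biased upwards, most at the lowest doses; if the assay is specific, the bias is zero. The documents do not say which case applies to any of the three products.

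The sizes are illustrations resting on the assumed profile, a constant endogenous level and full cross-reactivity. The ranking is firmer than any single figure: the bias is minor when drug greatly exceeds baseline and large when it does not, and half-life is sensitive to the choice of kel samples. The documents do not establish that low-dose exposure is mostly endogenous or that stage II dose selection would be misled.

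**What to change.** In SAP 8.4:

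- State for each product whether the assay reads endogenous erythropoietin, and give its LLOQ.
- Where it does, or where the pre-dose (PK1) value is measurable, also derive AUC, Cmax, kel, T1/2 and CL from each concentration minus the same volunteer's PK1 value.
- Set corrected values at or below zero to 0 for AUC and leave them out of the kel regression.
- Exclude from the kel regression any sample not clearly above PK1, and define 'clearly' before the data are seen.
- Report corrected and uncorrected parameters side by side.

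The cost is SAP wording and one extra derivation from a sample already planned, with no new volunteer, visit or blood draw. If PK1 is zero the subtraction changes nothing. The downside is that a constant subtraction may over- or under-correct if endogenous hormone changes after dosing. Showing both sets makes the size of the adjustment visible.
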